16.7 Data & Safety Monitoring

16.71 Safety review

The principal investigator(s) and the study statistician will review the study monthly to identify accrual, adverse events, and any endpoint problems that might be developing. The Mayo Clinic Cancer Center (MCCC) Data Safety Monitoring Board (DSMB) is responsible for reviewing accrual and safety data for this trial at least biannually, based on reports provided by the MCCC Statistical Office.

16.72 Adverse Event Stopping Rules

The stopping rules specified below are based on the knowledge available at study development. We note that the Adverse Event Stopping Rule may be adjusted in the event of either (1) the study re-opening to accrual or (2) at any time during the conduct of the trial and in consideration of newly acquired information regarding the adverse event profile of the treatment(s) under investigation. The study team may choose to suspend accrual because of unexpected adverse event profiles that have not crossed the specified rule below.

Accrual will be temporarily suspended to this study if at any time, we observe events considered to be at least possibly related to study treatment (i.e., an adverse event with attribute specified as “possible”, “probable”, or “definite”) that satisfy the following:

- If at any time, 4 of the initial 10 treated patients or 40% or more of all patients (i.e., when accrual is greater than 10 patients) have experienced a Grade 4+ adverse event at least possibly related to study treatment. per NCI Common Terminology Criteria for Adverse Events v.5.0, excluding the following:
 - Grade 4 white blood cell decreased lasting ≤ 3 days
 - Grade 4 platelet count decreased lasting ≤ 3 days
 - Grade 4 electrolyte alteration* lasting ≤ 3 days

*Electrolyte alterations include the following events in SOC
“Metabolism and nutrition disorders”

- Hyperglycemia or Hypoglycemia
- Hyperkalemia or Hypokalemia

We note that we will review Grade 4 and 5 adverse events deemed “unrelated” or “unlikely to be related”, to monitor the emergence of a previously unrecognized treatment-related adverse event.

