7.5 Safety Run-in for first six patients

Patients will receive futibatinib and pembrolizumab combination. The safety profile of both agents has been previously evaluated individually^{21,40}. To ensure the safety of this combination, we will perform a safety run-in with 6 patients. If there are 2 or more patients out of 6 who developed excessive toxicity during first cycle, the trial will be temporarily closed for enrollment to allow the study team to convene and discuss the best next steps.

7.51 For this protocol, excessive toxicity will be defined as follows:

Adverse event at least possibly related to the study medication	Definition using CTCAE v5.0
Any*	Grade 3 resulting in treatment interruption of both drugs for more than 21 days
Blood and lymphatic system disorders: Anemia	Grade 3 lasting >3 days
Any*	Grade 4
Investigations: Absolute neutrophil count decreased	Grade 4 lasting >7 days
Any	Grade 5
Gastrointestinal disorders 
 • Diarrhea • Nausea • Vomiting 	Grade 3 lasting >3 days with optimal supportive care

*Exceptions for: anemia, absolute neutrophil count; transient laboratory values without clinical manifestation; bowel obstruction resulting in hospitalization as a consequence of disease; which will not count as excessive toxicity

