16.3 Sample Size

We plan to accrue 22 evaluable patients. Evaluable patient is defined as those who are eligible, consented, are positive for FGF19, received any protocol treatment, and are without major violation. With 22 evaluable patients, we have 80% power to detect PFS6 from 25% (historical control) to 47%, assuming a 1-sided significance level of 0.1 and an accrual rate of 2 patients per month.

The trial has a single interim analysis for futility and the overall type I error rate is controlled. The interim analysis will be considered non-binding. The accrual will not be halted for the interim analysis.

We anticipate accruing an additional 3 patients to account for ineligibility, cancellation, major treatment violation, or other reasons. Therefore, maximum accrual is projected to be 25 patients. Sample size calculation was based on simulation using R.

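### Section 16.72 gives related deaths no threshold of their own: Grade 5 is pooled with Grade 4 at 4 of the first 10 patients, then 40%, so outside the run-in several related deaths need not suspend accrual

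*Combined protocol and SAP*

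**What the plan says.** Section 16.72 opens its rule with "Accrual will be temporarily suspended to this study if at any time, we observe events considered to be at least possibly related to study treatment". The condition is that "4 of the initial 10 treated patients or 40% or more of all patients" (the percentage applies once accrual passes 10) "have experienced a Grade 4+ adverse event at least possibly related to study treatment". Three Grade 4 laboratory findings lasting no more than 3 days are excluded. Nothing in the rule treats Grade 5 differently from Grade 4. Section 16.5 tabulates operating characteristics for the efficacy design; none are given for this safety rule.

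Other provisions that bear on deaths:

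- **Run-in, Section 7.5.** Enrollment closes temporarily on this condition: "If there are 2 or more patients out of 6 who developed excessive toxicity during first cycle". The table introduced by "excessive toxicity will be defined as follows" lists any related Grade 5 event.
- **Discretion, Section 16.72.** "The study team may choose to suspend accrual because of unexpected adverse event profiles that have not crossed the specified rule below". The section also allows the rule to be adjusted during the trial.
- **Reporting, Section 10.52.** A death within 30 days of the last dose, whatever its attribution, and a later death at least possibly related, must be reported within 24 hours.
- **Review, Section 16.71.** The principal investigator and statistician "will review the study monthly to identify accrual, adverse events", and the DSMB reviews accrual and safety at least biannually.

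Section 16.3 states that "maximum accrual is projected to be 25 patients".

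**The concern.** A 40% limit may be a defensible tolerance for related Grade 4 events in advanced HCC. Because Grade 5 is counted in the same tally, it also becomes the tolerance for treatment-related death, and the plan does not say that this was intended.

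The setting makes this matter. Section 1.2 states that there are no clinical data on futibatinib in HCC, alone or with immunotherapy. Sections 3.15 and 3.17 admit ECOG 2 and Child-Pugh B7. Section 1.4 explains that Amendment 4 opened the trial to patients who cannot have the standard first-line regimens. If related deaths occurred, patients could go on entering the trial, and whether anyone paused to look would rest on judgement rather than on a rule.

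**Working it through.** **Inputs.** The threshold and event definition come from Section 16.72, the maximum of 25 patients from 16.3, and the run-in rule from 7.5. True related-death rates are not in the documents, so a range is assumed.

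**1. Boundary as a count.** With n patients treated, the rule triggers at b(n) = 4 for n ≤ 10 and b(n) = 0.40 × n rounded up for n > 10. Since 4/10 = 40%, the two parts agree where they meet.

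| Patients n | Count that triggers |
|---|---|
| up to 10 | 4 |
| 11–12 | 5 |
| 13–15 | 6 |
| 16–17 | 7 |
| 18–20 | 8 |
| 21–22 | 9 |
| 23–25 | 10 |

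**2. Deaths that stay below it.** The largest counts without a trigger are 3 in 10 (30%), 5 in 15 (33%) and 7 in 20 (35%). The rule applies at any time, so 7 in 20 escapes only if the running count was at most 3 by patient 10, 4 by patient 12, 5 by patient 15 and 6 by patient 17. Each example assumes no related Grade 4 event in any other patient.

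**3. Chance that the rule ever triggers on deaths alone.** Let p be the true related-death rate and f(n, k) the probability of k deaths in n patients with no crossing so far. For k < b(n), f(n, k) = (1 − p) f(n − 1, k) + p f(n − 1, k − 1). The trigger probability is 1 minus the sum of f(25, k). This takes each outcome as known before the next patient enters.

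| Assumed related-death rate | Rule triggers by patient 25 |
|---|---|
| 5% | 0.1% |
| 10% | 1.4% |
| 15% | 5.7% |
| 20% | 14.6% |
| 25% | 28.3% |
| 30% | 45.2% |

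Most of this comes from the first ten patients: the binomial chance of at least 4 in 10 is 1.3% at p = 10% and 12.1% at p = 20%.

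**4. Dilution of a late signal.** The denominator is all patients. Suppose, purely as illustration, that the first 11 patients had no related Grade 4+ event and the next seven all died of related causes. The count is 7/18 = 38.9%, one short of the boundary of 8, so suspension is not required.

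**5. Whether another provision requires action.** The run-in covers Cycle 1 in six patients only. The discretion is optional and refers to unexpected profiles. The 24-hour duty calls for a report, not an accrual decision. The monthly team review has no death criterion. Reading biannual as every six months, the accrual of 2 patients per month in Section 16.3 allows 2 × 6 = 12 entries between DSMB reviews.

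**6. An any-death trigger, for comparison.** The chance of at least one related death in 25 patients is 1 − (1 − p)^25. At 1% it is 1 − 0.99^25 = 22.2%; at 10% it is 1 − 0.90^25 = 92.8%.

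**The case against.** The strongest reply is that deaths are handled in layers. They are reported within 24 hours, reviewed monthly by the team and periodically by the DSMB, and the team may suspend below the boundary or change the rule. Section 16.72 also commits to reviewing Grade 4 and 5 events judged unrelated. A related death would therefore be seen quickly. That stands, but visibility is not an obligation to pause or to convene the DSMB.

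The probabilities also rest on an extreme case in which every related Grade 4+ event is a death. Any related Grade 4 event in another patient counts toward the same boundary and raises the chance of a trigger. That stands too, so the figures describe the rule's sensitivity to deaths alone, not its overall performance.

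Timing limits the benefit. Section 1.4 reports 11 patients with FGF19 expression already enrolled at Amendment 4, so the run-in and the first-ten limb had passed. A new line affects later accrual only, but for those patients 16.72 is the only mandatory rule.

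Three stronger readings are tempting, and the documents do not support them:

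- *Three related deaths in the first ten could never stop enrollment.* Section 7.5 would close it if two fell in Cycle 1 among the first six patients. Of the 120 ways to place 3 deaths among 10 patients, 15 × 4 + 20 = 80 (66.7%) put at least two in the first six.
- *Nine related deaths in 25 would leave accrual untouched.* At 25 patients the projected accrual is complete. With outcomes known in sequence, only 568,676 of 2,042,975 orderings (27.8%) avoid an earlier crossing.
- *Section 16.72 is laxer than the run-in because 40% exceeds 2 of 6.* The run-in covers one cycle, six patients and a different event list; 16.72 accumulates over all treatment and all patients. The two percentages are not comparable, and the sections do not contradict each other.

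**Conclusion.** The point holds in limited form. Section 16.72 sets no separate threshold for deaths at least possibly related to treatment, and outside the Cycle 1 run-in no other provision requires a pause or prompt DSMB review after one. On deaths alone the rule is insensitive: about a 1.4% chance of triggering at an assumed 10% related-death rate and about 15% at 20%. These figures assume 25 patients, no related Grade 4 events in other patients, and outcomes known before the next entry.

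This is a gap in trial-level monitoring and worth closing because closing it is cheap. It is not an internal contradiction, and it does not show that deaths would go unnoticed.

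**What to change.** Add one line to Section 16.72 giving Grade 5 events at least possibly related to study treatment their own mandatory trigger for prompt DSMB review. One option is to pause further accrual after any such death until the DSMB has reviewed it. The exact threshold is for the sponsor and DSMB to set. Keep the existing 40% rule for Grade 4+ events. State the new trigger's operating characteristics over a range of assumed death rates.

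The cost is one sentence in an amendment and an occasional short pause with an ad hoc review. Under an any-death trigger, the chance of a pause over 25 patients is about 22% at a 1% related-death rate and about 93% at 10%. With part of the accrual already complete, the chance over the remaining patients is smaller.

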16.8 Subset Analyses for Minorities

16.81 Study availability

This study will be available to all eligible patients, regardless of gender, race or ethnic origin.

16.82 Statistical analysis by subset

There is no information currently available regarding differential effects of this regimen in subsets defined by race, gender, or ethnicity, and there is no reason to expect such differences to exist. Therefore, although the planned analyses will look for differences in treatment effect based on racial groupings, the sample size is not increased in order to provide additional power for subset analyses.

16.83 Regional population

The geographical region served by MCCC has a population which includes approximately 3% minorities. Expected sizes of racial by gender subsets are shown in the following table:

Accrual Targets			
Ethnic Category	Sex/Gender		
	Females	Males	Total
Hispanic or Latino	1	1	2
Not Hispanic or Latino	11	12	23
Ethnic Category: Total of all subjects	12	13	25
Racial Category			
American Indian or Alaskan Native	1	0	1
Asian	0	1	1
Black or African American	1	0	1
Native Hawaiian or other Pacific Islander	0	1	1
White	10	11	21
Racial Category: Total of all subjects	12	13	25

Ethnic Categories: **Hispanic or Latino** – a person of Cuban, Mexican, Puerto Rican, South or Central American, or other Spanish culture or origin, regardless of race. The term “Spanish origin” can also be used in addition to “Hispanic or Latino.”

Not Hispanic or Latino

Racial Categories: **American Indian or Alaskan Native** – a person having origins in any of the original peoples of North, Central, or South America, and who maintains tribal affiliations or community attachment.

Asian – a person having origins in any of the original peoples of the Far East, Southeast Asia, or the Indian subcontinent including, for example, Cambodia, China, India, Japan, Korea, Malaysia, Pakistan, the Philippine Islands, Thailand, and Vietnam. (Note: Individuals from the Philippine Islands have been recorded as Pacific Islanders in previous data collection strategies.)

Black or African American – a person having origins in any of the black racial groups of Africa.

Native Hawaiian or other Pacific Islander – a person having origins in any of the original peoples of Hawaii, Guam, Samoa, or other Pacific Islands.

White – a person having origins in any of the original peoples of Europe, the Middle East, or North Africa.

17.0 Pathology Considerations/Tissue Biospecimens

17.1 Summary Table of Research Tissue Specimens to be Collected for this Protocol

Research Study (Section for more information)	Specimen Purpose (check all that apply)	Mandatory or Optional	Type of Tissue to Collect	Block, Slides, Core, etc. (# of each to submit)	At any time after Reg*	At time of disease progression	Process at site? (Yes or No)	Temperature Conditions for Storage /Shipping
FGF-19 Testing, and correlative studies including Immunohistochemistry (Section 17.2 and 17.3)	 Eligibility  Correlative	Mandatory	Formalin Fixed Paraffin Embedded	2 cores (or archived 5 unstained slides)*	X		No	Ambient
Patient-derived tumor organoid culture and studies (Section 17.2 and 17.3) Rochester ONLY	 Correlative	Mandatory	Fresh Tissue	4-6 cores or pieces of tissue	X		No	Cold, ice pack
Tumor tissue at disease progression**	 Banking	Optional	Formalin Fixed Paraffin Embedded	3 cores or 10 unstained slides		X	No	Ambient

*All patients should have baseline biopsy for FGF-19 testing and correlative studies. If archived tissue is available and used for FGF-19 testing, then eligible patients will still need a baseline biopsy to collect correlative tissue unless already collected under IRB 17-003174. If baseline biopsy cannot be done (e.g., because not medically feasible or lack of lab capacity), and PI agrees, patient is still eligible if archived tissue is available for FGF-19 screening.

**If biopsy or surgery is done at time of disease progression for clinical reasons, a sample of tumor tissue is requested for comparison with baseline sample

17.2 Tissue Collection

17.2.1 Tissue Kits will not be provided for this protocol.

All patients should have baseline biopsy for FGF-19 testing and correlative studies after Preregistration.

If archived tissue is available and used for FGF-19 testing, then eligible patients will still need a baseline biopsy to collect correlative tissue prior to starting treatment unless already collected under IRB 17-003174.

If baseline biopsy cannot be done (e.g., because not medically feasible or lack of lab capacity), and PI agrees, patient is still eligible if archived tissue is available for FGF-19 screening.

17.23 Fresh Tissue

- 17.231 Six cores of fresh tumor tissue will be collected after registration and prior to Cycle 1 Day 1 of treatment.
- 17.232 Tissue must be labeled with the protocol number, study patient ID number, and the time and date of the biopsy.
- 17.233 Fresh tissue must be collected according to the table above.
- 17.234 A portion of the fresh tissue should be routed and made into formalin-fixed, paraffin-embedded (FFPE) blocks
- 17.234 Fresh tissue must be stored in tissue media on cold ice pack (~0°C) until delivery to the lab

17.24 Paraffin Embedded Tissue

- 17.241 One block of HCC tumor tissue from research biopsy will be submitted after registration and prior to Cycle 1 Day 1 of treatment.
- 17.242 Paraffin embedded tissue must be labeled with the protocol number, study patient ID number, and the time and date of the biopsy.
- 17.243 Paraffin embedded tissue must be collected and shipped according to specific instructions provided in the table above.
- 17.244 Paraffin embedded tissue can be stored at ambient temperature.

17.25 Submission/Shipping

- 17.251 Verify that ALL sections of the Tissue Specimen Submission Form (see Forms Packet), BAP Requisition Form (provided in kit), and specimen collection labels are completed and filled in correctly. Enter information from the Tissue Specimen Submission Form into the remote data entry system within 7 days after specimen collection (see Forms Packet).
- 17.252 Rochester ONLY: Fresh tissue specimens collected in tissue media should be placed on cold ice pack (~0°C) and immediately delivered to the following laboratories at Mayo Clinic in Rochester, MN:
[REDACTED]

17.26 Processing

- 17.261 Paraffin embedded tissue block
DLMP or BAP/PRC Shared Resource will process the paraffin embedded tissue specimens according to routine protocols.
Study Coordinator will route blocks to [REDACTED]
[REDACTED] that sample is on the way by email [REDACTED]
Rochester internal address: [REDACTED]

From outside of Rochester ship ambient and include room temperature cool pack if needed, to:

17.262 Fresh tissue cores – Rochester ONLY

17.2621 The laboratory of [REDACTED] will process half of the fresh tissue specimens.

Email [REDACTED] and copy [REDACTED] when you have a potential patient for the study (include patient name, MCN, diagnosis, biopsy location, and date/time of procedure, as well as study coordinator contact info) and then send a second email to confirm once the patient has consented.

On the day of the procedure, study coordinator will display/digital page the lab at [REDACTED] (do not priority page) when the procedure is about to start so the lab can send staff to collect tissue. Also contact lab directly at [REDACTED] to make sure the page is not missed.

17.2622 The laboratory of [REDACTED] will process half of the fresh tissue specimens.

Email [REDACTED] when you have a potential patient for the study (include patient name, MCN, diagnosis, biopsy location, and date/time of procedure, as well as study coordinator contact info) and then send a second email to confirm once the patient has consented.

On the day of the procedure, study coordinator will display/digital page [REDACTED] (do not priority page) when the procedure is about to start so the lab can send staff to collect tissue. Also contact lab directly [REDACTED] to make sure the page is not missed.

17.3 Background and Methodology

17.31 Patient-derived tumor organoid

Preclinical tumor models are important tools to study cancer biology, develop novel therapeutics, and provide information for treatment decisions. However currently available tumor models such as cell lines, transgenic mice and patient-derived xenograft (PDX) model have inherent limitations that can adversely affect the translation of preclinical findings to the clinic. Patient-derived tumor organoid is a 3-D cell culture which enables the establishment of *ex vivo* tumor model from scant core-needle biopsy specimen in a timely manner. These tumor organoids recapitulate both phenotypes and genotypes of the donor tumor. (Vlachogiannis et al. 2018) The laboratory of [REDACTED] at our institution has successfully established such tumor organoids from core-biopsy tumor specimens donated by patients with metastatic cholangiocarcinoma.

The established tumor organoids were ready for drug screening and related molecular studies within 4-6 weeks of the biopsy. Though the concordance between treatment effect in tumor organoids and the clinical benefit observed in the donor patients have been reported, the role of tumor organoids has not been prospectively evaluated in clinical trials of patients with advanced HCC. Here, we aim to 1) determine if drug response from a parallel *ex vivo* trial using patient-derived tumor organoid correlates with clinical response to futibatinib plus pembrolizumab and 2) to evaluate the role of thymidine kinase 1 in predicting the clinical response to treatment and discover potential mechanisms of resistance and sensitivity.

18.0 Records and Data Collection Procedures

18.1 Submission Timetable

Data submission instructions for this study can be found in the Data Submission Schedule.

18.2 Survival Follow-up/Event Monitoring

See [Section 4.](#)

18.3 CRF completion

This study will use Medidata Rave® for remote data capture (rdc) of all study data. Data collection for this study will be done exclusively through the Medidata Rave® clinical data management system. Access to the trial in Rave is granted through the iMedidata application to all persons with the appropriate roles assigned in Regulatory Support System (RSS). To access Rave via iMedidata, the site user must have an active account and the appropriate Rave role (Rave CRA, Read-Only, Site Investigator) on the organization roster at the enrolling site.

18.4 Site responsibilities

Each site will be responsible for ensuring that all materials contain the patient's initials, MCCC registration number, and MCCC protocol number. Patient's name must be removed.

18.5 Supporting documentation

This study requires supporting documentation for evidence of response to study therapy and progression after study therapy. These documents should be submitted within 14 days after the visit at which response or progression is determined.

Results of genomic testing should be uploaded when they are available.

Imaging reports for PET/CT or PET/MRI as well as for standard imaging should be uploaded within 14 days after the visit.

